16.0 Audio/Video Recording/Photography

We will not be performing any video, audio, or photographic recording of subjects, but may request pictures of telomeres from diagnostic laboratory.

17.0 Potential Benefits of this Research:

There has been a growing number of empirical studies of Chinese calligraphic handwriting that resulted in improvements in visual attention and span, increased mental concentration, confirmation as an effective treatment for psychosomatic conditions and post-traumatic hyper-arousal symptoms, and exhibiting significant effects on hypertension and type 2 diabetes. Leisure activities occurring later in life that include calligraphy writing may inhibit cognitive decline.

Our own studies clearly documented improvement in Wellbeing Scores (Rand SF-36 questionnaire), improvement in pain scores (McGill pain questionnaire) in subjects suffering from chronic pain, and improvement in depression scores (BDI, PHQ9 and HAM questionnaires) in patients with depression. Our reports have been published and presented at conferences.

18.0 Potential Risks to Participants:

No risks or negative side effects of the blessings given to human participants or calligraphy meditation with Tao Calligraphy have been observed in our previous pilot projects and formal studies.

19.0 Provisions to Protect Participant Privacy and Data Confidentiality:

All scientific data will be stored in the computer in spreadsheet under ID code numbers according to Tri Council Policy Statement: Ethical Conduct for Research Involving Humans (2005).

A unique ID code number will be assigned to each participant for entry for internal tracking. Once the unique ID number is assigned, no personal identity information is kept with research spreadsheets.

The data collected via website will have only confidential ID assigned and never any names or personal identifiers. As there are no names associated with participants' responses in their electronic research files on the website, it would be impossible to know which subject these responses belong to. These data are periodically downloaded and originals are deleted from the website for extra layer of precaution.

When client provides medical or personal information in paper form, these are scanned and forwarded to research team by email. Paper original documents are returned to participant who provided them. Once the email with documents is received by the research team, downloaded to a dedicated research external hard drive, and confirmed receipt, the emails with files are deleted from email inbox.

All collected personal and medical information is stored on external hard drive that can be accessed only through a password-protected computer.

There will be no hard copies of data printed out, although the results of statistical tests and actual papers for presentation will be in paper form.

20.0 Data Monitoring Plan to Ensure the Safety of Participants:

The collected data will remain the property of Sha Research Foundation and only members of the research team will have the access to the research data collected.

Each participant will complete an Application Form. The signed consent forms will be emailed or faxed to the Foundation. Data collection will be executed at 0, 3, and 9-month intervals after receiving the energy transmission, for a total of 9 months.

Research Data

At the time of admission to the study, participants will provide following:

1) Application that includes information of their illnesses and medications, and consent

2) Laboratory assessment of Telomere Length in Peripheral Blood Leucocytes. Results of analysis will be stored at Repeat Diagnostics, [name] for Telomere Assessment. Reports will be issued to clinical Principal Investigator [name], will be scanned and electronic copy will be stored on external hard drive, the paper version will be destroyed.

3) Data from

1. John Ware's SF-36 Quality of Life questionnaire

2. Simple Follow up Questionnaire of our design

The data collected via website will have only confidential ID assigned and never any names or personal identifiers. As there are no names associated with participants' responses in their electronic research files on the website, it would be impossible to know which subject these responses belong to. These data are periodically downloaded and stored on external hard drive; originals are deleted from the website for extra layer of precaution.

C) Data Processes

There will a Consent Process form filled after consenting procedure. This will be reviewed. All applications are audited for completeness.

The log of adverse events will be maintained. (This would also include data issues.)

The other logs would be Protocol Deviation Log, Subject Withdrawal and Termination Log, Subject Visit Log spreadsheet, and Telephone Log.

Application and consent will be scanned and stored on large (not flash drive) external drive by principal investigator. After he confirms receipt, any person obtaining these documents will delete them from their computers and from email inbox. Once principal investigator downloads the data from inbox to a hard drive, any email containing data will be deleted from his inbox.

Research Data collected on password protected entry on the website, will have only first name and confidential ID as identifiers, and so even in unlikely event of breach to website, no research data could be attributable to a particular person. These are downloaded to external hard drive and periodically deleted from website.

All data will be stored for 7 years and will be safely deleted afterwards. Any retiring hard drive will be not only safely erased using military protocol 3 wipe repetition and filling drive with Zeros (Program Avast), but also physically damaged so could not be read from anymore (in accordance with Canadian Medical Protective Association guidelines).

21.0 Long-term Data and Specimen Storage and Sharing:

All scientific data will be stored on external hard drive for at least 7 years under ID code numbers according to Tri Council Policy Statement: Ethical Conduct for Research Involving Humans (2005) and HIPAA. All data will be deleted after 7 years.

No personal or attributable medical data will be shared outside of Sha Research Foundation.

22.0 Qualifications of Research Team to Conduct the Research:

[name] [name], FRCS, neurosurgeon, affiliated as researcher with, and prior CEO of Sha Research Foundation. Previously as a Professor of Neurosurgery, University of Saskatchewan. Mailing address: Mt Seymour Clinic, [name]

The names of research participants removed as per Clinical Trials Gov website instructions.

23.0 Publication of the Research:

Authorship eligibility guidelines and any intended use of professional writers

We will follow ICMJE - International standards for reporting research: https://phcogcommn.org/wp-content/uploads/2021/08/icmje-recommendations.pdf

Authorship of the data of this study will be based on:

- 1. degree of contribution to the conception or design of the study
- 2. degree of creating any important intellectual content of the study
- 3. degree of participation on creating final report
- 4. an agreed role in the conduct of the study.

The results of the study will be published on the Foundation website and in scientific meetings and journals. The audience is expected to be the health care, scientific, and integrative, complementary, and alternative medicine communities.

The research data, data on the reports delivered to PI, and results of the study remain the intellectual property of Sha Research Foundation.

The laboratory data and results of Telomere assessment stored at laboratory site will remain the property of Repeat Diagnostics, North Vancouver, BC, Canada.

24. Budget the Research:

Estimated total cost for 10 subject: \$10, 983 (in Vancouver) or \$14,323 (outside of Vancouver) plus \$3,185 legal fees (that are the same for both options).						
Legal and Study overhead cost:						
ITEM	COST	INFORMATION				
IRB ethics review and approval	\$2,635.00	Advarra				
Research protocol review fee	\$200.00	VCH cost				
Research protocol set up fee TOTAL OVERHEAD	\$350.00 \$3.185.00	VCH cost				

Specimen handling and testing:

Venipuncture Fee & specimen labeling/handling	\$50.00	
Specimen packaging* *See picture below for details	\$8.10-9.45	UN3373 shipping box: https://www.uline.ca/ Biological substance category B
FedEx priority specimen transportation	\$127.07	FedEx Priority overnight (Toronto - Vancouver) \$127.07 - delivery next business day
FedEx priority specimen transportation	\$91.05	Within Vancouver
Telomere length measurement - 2 cells *see attached requisitions for BC & Canada	\$400.00	Repeat Diagnostics [name]
Telomere length measurement - 6 cells	\$800.00	
TOTAL COST per 1 SUBJECT	\$549.15	Subject from Vancouver and using 2 cells Telomere length measurement.
TOTAL COST per 1 SUBJECT	\$716.15	Subjects outside of Vancouver using 2 cells Telomere length measurement, additional cost is 17\$ Family doc referral, 150\$ hematologist specialist order of test
TOTAL COST per 1 SUBJECT	949.15	Subject from Vancouver and using 6 cells Telomere length measurement

Appendices and additional documents:

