- Laboratory assessment of telomere Length in peripheral blood Leucocytes at the entry time point (Time 0), at the end of 3 months (Time 1), and at the end of 9 months (Time 2)
- Completion of the questionnaires by the participants at the entry time point (Time 0), at the end of 3 months (Time 1), and at the end of 9 months (Time 2)
- Completion of assessments by a Study principal and co-investigators

Data collection:

A Laboratory Assessment:

Laboratory assessment of Telomere Length in Peripheral Blood Leucocytes

Blood samples will be drawn at DAP accredited institution in British Columbia (Life Labs or Vancouver Coastal Health) or another accredited institution in Canada and will be promptly sent by currier to Repeat Diagnostics, [name] for Telomere Assessment. Reports will be issued to clinical Principal Investigator [name]

All participants will have blood samples drawn at the entry time point (Time 0), at the end of 3 months (Time 1), and at the end of 9 months (Time 2).

B Improvement of general well-being or clinical well-being as measured by standardized questionnaires

These questionnaires will be used in the study:

- 1. John Ware's SF-36 Quality of Life questionnaire
- 2. Simple Follow up Questionnaire of our design

All participants will complete questionnaires at the entry time point (Time 0), at the end of 3 months (Time 1), and at the end of 9 months (Time 2).

Study Execution

The study will be performed by collecting enrollment data and medical data directly from patients personally, over the phone, via email, or on-line (Zoom). The research Questionnaires will be filled on-line using personal ID Codes – to ensure confidentiality. The codes will be emailed by the PI to each of the participants individually.

Data collection, data handling, and data assessment will be the responsibility of the Sha Research Foundation's research team members who have a medical, nursing, and/or scientific background, and will be performed through personal delivery, by email and online collection.

Members of the research team will NOT administer any transmission of pure energy (blessing) or any form of medical support to participants of the study.

Transmission of pure energy and instruction of subjects on how to practice meditations with Tao Calligraphy will be the sole responsibility of Universal Soul Service Corp.

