The transmission of pure energy (blessing) will be done to participants for free by Tao Academy certified teacher remotely. There will be no fees for the teaching on how to meditate nor for any other aspect of participation in the study. Conversely, participants will receive no remuneration for participating in the study.

A copy of Tao Calligraphy Greatest Love and Meditation with Tao Calligraphy instruction sheet will be provided to the participants electronically.

Participants of the study will be required to self-meditate using the Tao Calligraphy for thirty minutes twice every day and to record the length of practice and responses during and after each practice. Besides individual meditations on their own, participants will attend once a week 30-minute-long group meditation practice sessions led by an instructor, done over the Zoom platform.

Subjects in the study should continue to follow their physicians' advice and recommendations during their participation in the study and should continue to receive any and all conventional treatment in which they have been participating prior to entry into this study.

Sha Research Foundation will clearly inform participants that the teaching and research teams are not offering any medical diagnosis, guidance, evaluation, or treatment, and that participation in the study is not a replacement for any conventional medical treatments or diagnosis.

Participants are also encouraged to continue their usual spiritual practices in which they have been participating prior to the study.

Participants of the study will be responsible for informing the research team of any and all of their illnesses and medications taken, but NO copies of their medical records from their medical practitioners or specialists will be collected besides telomere reports.

The study will commence in 2023 and will last for about 2 years. The plan is to accept new subjects into the study at any time from its commencement in 2023 up to 2 years later (from April of 2023 with expected conclusion in December of 2025).

A minimum of 10 and a maximum of 20 subjects may be admitted to this study during the study years. Subjects can withdraw from the study with no penalty at any time for whatever reasons they may have.

3.0 Enrollment Criteria (who can be in your study and who would not be eligible to participate in your study):

Patient Population

Inclusion criteria

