Sha Research Foundation Twitter and Facebook social media.

Newspaper and magazine advertisements.

We are submitting previously approved letter and advertisement for the study Pro00031067.

SCREENING METHODS:

Member of the research team will contact candidates for the research study over the phone, set up zoom interviews, conduct discussions (clarification of inclusion / exclusion criteria), help with signing of the consent /Information, and offer instruction in the study design.

Successful applicants will sign the consent and forward it to clinical / research principal investigators.

6.0 Research Locations:

[name] [name] [contact] / [contact]

7.0 Multi-site Research (research that involves external collaborating institutions and individuals):

N/A			

8.0 International Research (where data collection will occur outside the United States and U.S. territories, including online activities)

This pilot research will take place in Canada exclusively.

9.0 **Procedures Involved:**

The study is conducted on an outpatient basis and includes:

• A personal or telephone discussion (clarification of inclusion / exclusion criteria) signing of the consent /Information.

- instruction in the study design and practicing the Tao Calligraphy-tracing meditation;
- first data collection questionnaires at Time 0
- Blood sample drawn and telomere assessment at Time 0.
- regular Zoom practices with participants in the intervention group (or prerecorded meditation practices with certified teachers as a back-up)
- Completion of the questionnaires by the participants at Time 1 (3 months)
- Blood sample drawn and telomere assessment at Time 1 (3 months)
- Completion of the questionnaires by the participants at Time 2 (9 months)
- Blood sample drawn and telomere assessment at Time 2 (2 months)
- Completion of assessments by a Study principal co-investigator

10.0 Research with Vulnerable Populations (if children are the ONLY vulnerable population you plan to enroll, do NOT complete this section -- instead fill out Appendix A)

N/A

11.0 Incomplete Disclosure or Deception:

N/A

12.0 Consent Process:

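### Does the cost estimate for 10 subjects, which prices 20 blood draws where 30 are scheduled, call for a change to the plan?

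*Combined protocol and SAP*

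**What the plan says.** The Method section, under Data collection, has blood drawn from all participants "at the entry time point (Time 0), at the end of 3 months (Time 1), and at the end of 9 months (Time 2"). Section 9.0 also lists three draws, though it labels the last one "Blood sample drawn and telomere assessment at Time 2 (2 months"). Section 20.0 states: "Data collection will be executed at 0, 3, and 9-month intervals after receiving the energy transmission, for a total of 9 months". That sentence concerns data collection in general; the laboratory assessment named in Section 20.0 is listed under admission. Study Execution says: "A minimum of 10 and a maximum of 20 subjects may be admitted to this study".

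Section 24 prices the specimen work item by item and gives three unit totals, each labelled "TOTAL COST per 1 SUBJECT": $549.15 (Vancouver, 2 cells), $716.15 (outside Vancouver, 2 cells) and $949.15 (Vancouver, 6 cells). The note to the second begins "Subjects outside of Vancouver using 2 cells Telomere length measurement, additional cost is" and adds $17 for a family doctor's referral and $150 for a specialist's order. Courier cost is listed twice: $127.07 for Toronto to Vancouver, and $91.05 marked "Within Vancouver". The headline total, introduced as "Estimated total cost for 10 subject", does not say how many draws it covers.

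**The concern.** Telomere length is the study's main laboratory measure, and Section 24 is the only costing of it in the text I could read. A figure that covers two rounds of blood work out of three suggests that the 9-month round was not provided for. If money ran out after the second round, the 9-month telomere result would be missing for the whole cohort, and the planned follow-up comparison would rest on baseline and 3 months alone. The mislabelled third draw in Section 9.0 adds to the impression that the last visit was not thought through.

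**Working it through.** **Inputs (Section 24).** Venipuncture and handling $50.00; packaging $8.10 to $9.45; courier $91.05 or $127.07; 2-cell assay $400; 6-cell assay $800; referral and ordering fees $17 + $150 = $167; overhead $2,635 + $200 + $350 = $3,185. Draws per subject: 3 (Method; Section 9.0).

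**Reproducing the unit costs**
- Vancouver: 50 + 8.10 + 91.05 + 400 = 549.15, as printed.
- Outside: 549.15 + 167 = 716.15, as printed. This carries the lower courier price.
- 6 cells: 50 + 8.10 + 91.05 + 800 = 949.15, as printed.

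Each unit holds the items of a single draw and uses the low end of the packaging range.

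**Reproducing the headline**
- 20 × 549.15 = 10,983.00, as printed.
- 20 × 716.15 = 14,323.00, as printed.
- 10,983 / 949.15 = 11.57, not a whole number, so the 2-cell price was the one budgeted.

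For 10 subjects, 20 units means two draws each.

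**Cost of 10 × 3 = 30 draws, before overhead**

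| Case | Calculation | Cost | Gap to headline |
|---|---|---|---|
| Vancouver | 30 × 549.15 | 16,474.50 | 5,491.50 |
| Outside, fees once per subject | 16,474.50 + 10 × 167 | 18,144.50 | 3,821.50 |
| Outside, fees at every draw | 30 × 716.15 | 21,484.50 | 7,161.50 |
| Outside, fees at every draw, courier 127.07 | 30 × (716.15 − 91.05 + 127.07) = 30 × 752.17 | 22,565.10 | 8,242.10 |

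The high end of the packaging range adds at most 30 × 1.35 = 40.50.

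**Can a kinder reading close the gap?**
- Vancouver: no. The assay fees alone are 30 × 400 = 12,000, above 10,983.
- Outside, fees once per subject and one courier consignment per round: 30 × (50 + 8.10 + 400) + 3 × 127.07 + 1,670 = 15,794.21, still above 14,323.
- Outside, with the fees also dropped: 15,794.21 − 1,670 = 14,124.21, just under 14,323. This contradicts the printed 716.15, which includes the fees.

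**Does anything in the trial use the figure?** Section 4.0 sets 10 to 20 subjects without reference to cost and leaves the power calculation to a later randomised study. The hypothesis and analysis text in Section 1.0 and the analysis paragraph in Section 4.0 do not use it. The Method section and Section 9.0 schedule the third draw without any condition on funds.

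**The case for a change.** The best case for a change is that the mismatch is exact in both locations, so neither rounding nor damage to the table explains it. A correction would cost only a few lines of text. A sponsor that set aside the headline sum would be short by one round in three, and that round would be the 9-month one. If 20 subjects enrol, 60 draws in Vancouver cost 60 × 549.15 = $32,949.

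The arithmetic stands, and so do two smaller points: the unit totals are labelled per subject but priced per draw, and the outside-Vancouver unit uses the courier price listed for Vancouver.

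The step from there to lost data does not stand. Nothing in the readable text makes the estimate a ceiling or lets a draw be skipped for want of money. The requisitions cited in the table were not available to me.

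Some wider charges also fail. Twenty units could in principle mean 20 subjects with one draw each, but the heading says 10, and one draw cannot measure change. The choice of assay in the budget is not open, since only the 2-cell price gives the printed totals. The mislabelled third draw sits directly below a line that puts the Time 2 questionnaires at 9 months, and the Method section agrees with 9 months. It is a typing slip and leaves the count at three.

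**Conclusion.** The estimate in Section 24 covers 20 of the 30 draws that 10 subjects require. It is short by $5,491.50 in Vancouver. Outside Vancouver it is short by between $3,821.50 and $7,161.50 at the freight built into the printed unit, or by up to $8,242.10 at the listed Toronto price. These figures assume 10 subjects, the 2-cell assay, the low end of the packaging range and no overhead.

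This is a clerical error in an administrative section. The schedule of draws is clear without it, no statistical quantity depends on it, and the text does not show that any assay would be lost. The sponsor may tidy the sum and the label on the third draw at the next revision, but neither edit would affect the conduct, analysis or interpretation of the trial. No change to the plan is needed.

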Telomerase activity was significantly greater in retreat participants than in controls at the end of the retreat (p < 0.05). Increases in Perceived Control, decreases in Neuroticism, and increases in both Mindfulness and Purpose in Life were greater in the retreat group (p < 0.01). Mediation analyses indicated that the effect of the retreat on telomerase was mediated by increased Perceived Control and decreased Neuroticism. In turn, changes in Perceived Control and Neuroticism were both partially mediated by increased Mindfulness and Purpose in Life. Additionally, increases in Purpose in Life

ⁱ In an evaluation of minimally invasive sample collection methods for telomere length measurement, Oragene saliva was moderately correlated ($\rho = 0.48$, p = 0.002) and the most similar in size to buffy coat from venous blood, considered the "gold standard." [17]

directly mediated the telomerase group difference, whereas increases in Mindfulness did not.

[25] C. Dal Lin et al.: 2021, Rapid changes of miRNAs-20, -30, -410, -515, -134, and -183 and telomerase with psychological activity: A one year study on the relaxation response and epistemological considerations. Journal of Traditional and Complementary Medicine

Telomerase is a cellular enzyme that adds the necessary telomeric DNA (T_2AG_3 repeats) to the 3 '-end of the telomeres, protecting their degeneration. 74 The activity of this enzyme represents a marker of cellular aging75 and is implicated in aging-associated diseases. 76 However, compared to telomere length, telomerase function seems to correlate more faithfully with stress-related psychological mechanisms. 75 Stress leads to a decrease in its activity77 while relaxation favors its functioning,78 as our results appear to confirm.

The telomerase activity (Fig. 3) appeared to increase during the RR sessions (p < 0.01 Wilcoxon test at every time point) both in patients and in healthy volunteers. No significant variation was found in the CONTROLS (p > 0.05 Wilcoxon test at every time point). The basal values (before and after 20 min) of telomerase activity were comparable in all groups and were merged into a single starting basal point. Micro-RNAs of cardiovascular interest, involved in cell senescence and in the NF- κ B network (miRNAs -20, -30, -410, -515, -134, and -183), and the activity of telomerase in peripheral blood mononuclear cells (PBMCs) were measured in the serum of patients with ischemic heart disease (and healthy controls) immediately before and after a relaxation response session (RR), three times (after the baseline), in one year of follow-up. Results: miRNA-20 and -30 levels and PBMCs-telomerase activity increased during the RR while the -410 and -515 levels decreased. During the RR sessions, both miRNA-134 and -183 decreased.

The orientation of mental processes, either toward stress or toward relaxation, can impact cellular ageing through at least three main recognized pathways: the immune system,⁷⁰ the oxidative balance,⁷¹ and the activity of telomerase.⁷² Although telomere length is implicated in cellular ageing, the evidence suggesting telomere length is a biomarker of ageing in humans is equivocal,⁷³ if not invalid.⁵⁷

As stated, we previously assessed malondialdehyde (oxidative-stress marker) and galectin-3 (immune system-inflammatory marker) levels as aging^{58,59} and cellular senescence markers, 60, 61, 62, 63 demonstrating a decrease in the course of RR.⁶⁴ Numerous studies in the literature and our previous studies^{12,19} have shown that RR causes a decrease in the levels of inflammatory cytokines, stress hormones, inflammatory genes expression,¹⁹ and epigenetic markers of ageing.²⁰

From **2017 Effect of heartfulness meditation on burnout, emotional wellness, and telomere length in health care professionals**, Journal of Community Hospital Internal Medicine Perspectives, [26]

ABSTRACT Background: Burnout poses significant challenges during training years in residency and later in the career. Meditation is a tool to treat stress-related conditions and promote wellness. Telomere length may be affected by burnout and stress. However, the benefits of meditation have not been fully demonstrated in health care professionals. Objective: We assessed the effects of a 12-week 'Heartfulness Meditation' program on burnout, emotional wellness, and telomere length in residents, faculty members, and nurses at a large community teaching hospital during the 2015–16 academic year. Methods: All subjects completed a baseline Maslach Burnout Inventory (MBI) and Emotional Wellness Assessment (EWA) at the beginning of the study. Meditators received instructions in Heartfulness Meditation. At week 12, subjects completed a follow up MBI and EWA scores. Salivary telomere length was measured at baseline and week 12. Results: Twenty-seven out of a total 155 residents (17.4%) along with eight faculty physicians and 12 nurses participated in the study. Thirty-five enrolled as meditators and 12 as controls. At 12 weeks, the meditators had statistically significant improvement in all measures of burnout and in nearly all attributes of EWA. Controls showed no statistically significant changes in either burnout or emotional wellness scores. Relative telomere length increased with statistical significance in a younger subset of meditators. Conclusion: Our results indicate that meditation offers an accessible and efficient method by which physician and nurse burnout can be ameliorated and wellness can be enhanced. The increased telomere length is an interesting finding but needs to be confirmed with further research. Abbreviations: EWA: Emotional wellness assessment; MBI: Maslach burnout inventory; EE: Emotional exhaustion; DP: Depersonalization.

From: Exploring Epigenetic Age in Response to Intensive Relaxing Training: A Pilot Study to Slow Down Biological Age

Abstract DNA methylation (DNAm) is an emerging estimator of biological aging, i.e., the oftendefined "epigenetic clock", with a unique accuracy for chronological age estimation (DNAmAge). In this pilot longitudinal study, we examine the hypothesis that intensive **relaxing training of 60 days** in (20) patients after myocardial infarction and in (10) healthy subjects may influence leucocyte DNAmAge by turning back the epigenetic clock. Moreover, we compare DNAmAge with another mechanism of biological age, leucocyte telomere length (LTL) and telomerase. DNAmAge is reduced after training in healthy subjects (p = 0.053), but not in patients. LTL is preserved after intervention in healthy subjects, while it continues to decrease in patients (p = 0.051). The conventional negative correlation between LTL and chronological age becomes positive after training in both patients (p < 0.01) and healthy subjects (p < 0.05). In our subjects, DNAmAge is not associated with LTL. Our findings would suggest that intensive relaxing practices influence different aging molecular mechanisms, i.e., DNAmAge and LTL, with a rejuvenating effect. Our study reveals that DNAmAge may represent an accurate tool to measure the effectiveness of lifestyle-based interventions in the prevention of age-related diseases.

References

- [2] Aunan JR, Cho WC & Soreide K, "The biology of aging and cancer: a brief overview of shared and divergent molecular hallmarks," *Aging Dis.*, vol. 8, p. 628–642, 2017.
- [4] Kalyani RR & Egan JM, "Diabetes and altered glucose metabolism with aging," *Endocrinol. Metab. Clin. North Am.*, vol. 42, p. 333–347, 2013.
- [5] Steenman M & Lande G, "Cardiac aging and heart disease in humans," *Biophys. Rev,* vol. 9, p. 131–137, 2017.
